### Pivot Breath Sensor.

The primary endpoint will assess any change in the proportion of participants' Stage of Change response at day 28 compared to baseline

- A positive outcome is defined as a participant responding as more ready to quit. For example, a change in response from seriously thinking of quitting smoking "...within the next 6 months" at baseline to seriously thinking of quitting smoking "...within the next 30 days" at day 28.

The secondary endpoints include:

- The proportion of participants who reported  $\geq 1$  quit attempt by day 28; will be compared to zero
  - A quit attempt is defined as answering  $\geq 1$  to the following question: "Since you began using the Pivot Breath Sensor, how many times have you tried to quit smoking where you've gone at least 1 day without smoking a cigarette, even a single puff?"
- The proportion of participants who reduced their cigarettes per day (CPD) by  $\geq 50\%$  by day 28, compared to baseline

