## **6.6 SAMPLE SIZE AND JUSTIFICATION**

This study will enroll up to 220 participants. Consideration for the sample size included powering the study to observe a clinically meaningful change from baseline for the primary and secondary endpoints using 80% power at a statistical significance of  $P < 0.05$ . The primary endpoint utilized preliminary data from a similar 37 participant pilot study. Data at the 14-day time point showed 31%, 66% and 3% of participants had increased, unchanged and decreased Stage of Change, respectively, from baseline. To detect a statistically significant change in these proportions requires enrolling 50 participants.

The estimated proportion of participants achieving  $\geq 1$  quit attempt is 25% based on interim results from the pilot study. Based on the median prevalence of 65.4% for past-year quit attempts in the general population [13], the average monthly quit attempt rate is approximately 5%. To show that a proportion of 25% of participants making a quit attempt by day 28 is statistically different from 5% will require  $n=16$ .

Finally, literature indicates approximately 1% of the general population [14-18] and 2-5% of individuals in cigarette reduction studies [19, 20] will reduce their CPD by  $\geq 50\%$  on a monthly basis. Assuming that 10% of participants in the present study reduce their CPD by  $\geq 50\%$  by day 28, the present study will require  $n=185$  to show a difference from 5%. Taking these analyses into consideration along with expected attrition, the present study will enroll up to 220 participants.

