## 10.2 ANALYSIS

Changes in measurements from baseline will be assessed at different timepoints in the study. Participants will serve as their own controls and comparisons will be made to no change. One sample t-test will be used for numerical data. Fisher's Exact or Chi square tests will be used for categorical data. Analyses will be conducted to calculate mean (SD) for normally distributed variables for actual data or mean (SE) for modeled data and median (interquartile range) values in instances of non-normally distributed variables.

McNemar test will be used for 2-category match-paired data. Cohen kappa statistic will be used for 3-category match-paired data. To evaluate changes in attitudes or cigarettes smoked per day over time, repeated measures linear mixed model analyses will be performed using a compound symmetric correlation matrix to model the repeated measures within subjects. To make specific comparisons across time, F statistics will be computed using the results from the model. Statistical significance is set at  $P < .05$ .

Analyses for the outcomes will be evaluated for only those who complete the survey (i.e. completer) and assessed to take into account missing data. To be included in any completer analysis the participant must provide a baseline response and the outcome response. For outcomes that are missing data, these will be assessed pending the data type.

For categorical data, the last response post-baseline will be carried forward for the day 28 analysis and the last response post-28 days will be carried forward for the day 84 assessment. If there is not any data to carry forward, the data will be considered unchanged from baseline. Numerical data will use linear mixed modeling.

All deviations from the study protocol will be identified, recorded and analyzed.

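### The primary Stage of Change endpoint does not say how participants who become less ready to quit are counted, and the analysis section names no test that would settle it

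*Combined protocol and SAP*

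**What the plan says.** Section 6.3 states: "The primary endpoint will assess any change in the proportion of participants' Stage of Change response at day 28 compared to baseline". This gives no direction. The bullet beneath it adds that "A positive outcome is defined as a participant responding as more ready to quit", with an example of moving from the 6-month answer to the 30-day answer. The opposite move is not mentioned.

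Section 6.6 sizes this endpoint on a 37-participant pilot: "Data at the 14-day time point showed 31%, 66% and 3% of participants had increased, unchanged and decreased Stage of Change, respectively, from baseline". It continues: "To detect a statistically significant change in these proportions requires enrolling 50 participants". The general standard in that section is "using 80% power at a statistical significance of" P < 0.05.

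Section 10.2 has participants serve as their own controls and says "comparisons will be made to no change". It lists Fisher's exact or chi-square tests for categorical data, McNemar for two-category paired data and Cohen kappa for three-category paired data. It does not say which applies to the primary endpoint. The Stage of Change item, given under the quota table in the eligibility criteria, has three answers: within 30 days, within 6 months, and not thinking of quitting.

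**The concern.** A single three-level answer given twice, 28 days apart, will move up in some people and down in others even if the sensor does nothing. The study has no control group, so the downward moves are the main internal information, though imperfect, on how much of the upward movement is noise. An endpoint that counts only improvers and compares them with none ignores that information: ordinary answer-switching would look like an effect, and so could a net shift away from quitting.

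The plan neither requires that analysis nor rules it out. The choice between it and a balanced paired test could be made after the data are seen, in an open-label study whose investigators hold equity in the sponsor (section 11).

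**Working it through.** **1. What the default rule gives.** Stage of Change at two times is three-category paired data, so section 10.2 points to Cohen kappa. Kappa depends on the diagonal of the table and the products of the margins, and both are unchanged if baseline and Day 28 are swapped. Illustration with assumed cells (rows baseline, columns Day 28, order not thinking / 6 months / 30 days): 0.10, 0.08, 0.01; 0.01, 0.20, 0.22; 0.00, 0.02, 0.36. This has 31% up and 3% down, and kappa = 0.457. The transposed table has 3% up and 31% down, and kappa is again 0.457. Kappa cannot serve as a test of improvement.

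**2. The plan's own n = 50.** Inputs from section 6.6: up 0.31, down 0.03, 80% power, 5% level (two-sided assumed). Movers total 0.31 + 0.03 = 0.34; the net difference is 0.31 − 0.03 = 0.28.

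- McNemar normal approximation: n = (1.96·√0.34 + 0.8416·√(0.34 − 0.28²))² / 0.28² = (1.143 + 0.430)² / 0.0784 = 31.6, so 32.
- Exact sign test on movers: power 77% at n = 32, 79% at 33, 81% at 34, 95% at 50.
- Other paired versions give 27 (t-test on a +1/0/−1 score) to 36 (continuity-corrected McNemar).

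None gives 50 at 80% power. The same section's secondary figures do reproduce with a one-sample proportion formula (null variance for the level, alternative variance for power): 25% versus 5% gives 15.7, so 16; 10% versus 5% gives 184.8, so 185. The stated 50 therefore does not reveal which primary analysis was intended.

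**3. The two readings under no net effect.** Assumptions: 185 responders (the section 6.6 requirement for the cigarettes-per-day endpoint) and random switching at 5%, 10% or 15% in each direction. The documents give no switching rate.

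Improvers judged against zero, with X ~ Binomial(185, p):

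| Rule for a positive result | Improvers needed | p = 5% | p = 10% | p = 15% |
|---|---|---|---|---|
| Any improver | 1 | 99.99% | >99.9% | >99.9% |
| Wald 95% CI excludes 0 | 4 | 98.4% | >99.9% | >99.9% |
| Fisher's exact against 0/185 | 6 | 90.4% | 99.99% | >99.9% |

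For the first row, 1 − 0.95^185 = 0.9999. For Fisher, 5 improvers give P = 0.061 and 6 give P = 0.030.

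Increases against decreases (two-sided exact sign test): significant in favour of improvement in 1.5%, 1.7% and 1.9% of trials at 5%, 10% and 15% each way.

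**4. Net worsening.** With 5% up and 15% down (assumed), the improver-only results are those in the 5% column, because decreases do not enter. The sign test shows significant worsening in 84% of trials and essentially never favours improvement.

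**5. Limits of the balanced test.** The 30-day answer cannot rise and the not-thinking answer cannot fall, so random switching need not be symmetric. Assume a baseline of 50% / 35% / 15% (30 days / 6 months / not thinking), which the quotas allow, and a 10% chance of each available one-step move. Expected moves are 0.10 × (0.35 + 0.15) = 5% up and 0.10 × (0.50 + 0.35) = 8.5% down. With 185 responders the sign test then declares worsening in about 19% of trials. At 60% / 25% / 15% the moves are 4% up and 8.5% down, and the figure is about 33%.

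**The case against.** The best defence is that the passages can be read together without conflict. The opening sentence of the endpoint states a comparison, the bullet labels the favourable direction, and a null of no change with participants as their own controls is naturally a paired null in which upward and downward moves balance. McNemar is on the section 10.2 list. Under that reading the false favourable rate is under 2% and the problem disappears. This stands as one permitted reading, but the plan does not select it, and its own rule for three categories leads to kappa.

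Three stronger conclusions that a reader might draw are not supported:

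- *That the plan tests improvers against zero.* Section 6.3 writes a comparison with zero only for quit attempts. For Stage of Change it is a possible reading, not the stated rule.
- *That section 6.6 is a third, conflicting definition.* It reports pilot results as a sizing basis and defines no endpoint. It does show that the team tabulates decreases.
- *That n = 50 came from a two-group formula.* Two groups of 25 can be obtained with an unpooled variance: 7.849 × (0.31×0.69 + 0.03×0.97) / 0.28² = 24.3 per group. But the pooled version gives 28 per group, a paired test at 95% power gives 51, and a 3-df symmetry test gives 48. The origin cannot be known from the documents.

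It is also fair to say that decreases are not a clean measure of noise on a three-level scale (step 5), and that a two-sided test can be significant in the unfavourable direction without being wrong.

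**Conclusion.** The concern holds as a gap in specification. The plan does not say how less-ready participants enter the primary endpoint, names no directional test for it, and gives a sample size that no paired increase-versus-decrease calculation tried here reproduces at 80% power.

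The consequence is conditional. If improvers were judged against zero, symmetric switching of only 5% each way would look positive in 90% to over 99.9% of trials, depending on the rule; the balanced test would favour improvement in under 2%. These figures rest on 185 responders and assumed switching rates. The mismatch over n = 50 is harmless to study size: 50 exceeds the 34 needed, and total enrolment is set by the cigarettes-per-day endpoint. This should be corrected before analysis.

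**What to change.** In sections 6.3 and 10.2, define the primary endpoint as the proportion of participants more ready to quit at Day 28 minus the proportion less ready, each relative to their own baseline. State a null of zero, a two-sided exact sign (McNemar-type) test on those who moved, and a 95% confidence interval. Allow a favourable conclusion only if the difference is positive. Exclude kappa as the test for this endpoint. Report the improved, unchanged and worsened percentages overall and by baseline stage, so that the floor and ceiling limits are visible.

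In section 6.6, restate the requirement on this test: about 34 participants for 80% power at 31% versus 3%, noting that 50 gives about 95%. The ceiling of 220 stays, because n = 185 for the cigarettes-per-day endpoint drives it.

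The cost is wording, with no new data or participants. There are three drawbacks. The headline is slightly less favourable (a net 28 points instead of 31% on the pilot figures). A baseline heavy in the 30-day answer can pull the net difference toward worsening. And in a single-arm study the test still cannot separate a sensor effect from general drift in readiness.

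### Section 6.3 tests the day-28 quit-attempt proportion against zero, while section 6.6 puts the background rate at about 5% a month and sizes the endpoint against 5%

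*Combined protocol and SAP*

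**What the plan says.** Section 6.3 (Study Outcomes) lists, as a secondary endpoint, the proportion of participants with at least one "quit attempt by day 28; will be compared to zero". The item behind it reads "Since you began using the Pivot Breath Sensor, how many times have you tried to quit smoking", with an attempt defined as at least one day without smoking.

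Section 6.6 (Sample Size and Justification) starts from a "median prevalence of 65.4% for past-year quit attempts in the general population" and concludes that "the average monthly quit attempt rate is approximately 5" percent. It then takes 25% from a pilot study and gives n=16 to show that the proportion "making a quit attempt by day 28 is statistically different from 5" percent.

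Section 10.2 (Analysis) gives a general rule, "Participants will serve as their own controls and comparisons will be made to no change", and a list of tests in which Fisher's "Exact or Chi square tests will be used for categorical data". It does not mention 5% and assigns no test or test value to this endpoint.

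**The concern.** One endpoint has two null values. The power statement concerns 5%; the stated comparison concerns zero.

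The item counts attempts since the participant began using the sensor, so everyone is at zero on day 1 by construction. Zero is where the counter starts, not the value expected if the sensor has no effect. On the plan's own figure, a sensor that did nothing would still be followed by about 5% of participants making an attempt.

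The general no-change rule in section 10.2 does not help, because no change from a counter that starts at zero is again zero.

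Rejecting the zero null would not be a type I error for that null as written. The trouble is that rejecting it is nearly certain on background attempts alone, so a significant result could be reported as an effect of the sensor when it carries no information about one.

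**Working it through.** **Inputs.** From section 6.6: background 5%, planning value 25%, power 80%, significance level 0.05, n=16 for this endpoint, n=185 for the endpoint of at least 50% reduction in cigarettes per day (CPD), maximum enrolment 220. Sidedness is not stated; two-sided is assumed. No attrition rate is given, so results are shown at n=185 and n=220.

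**1. Reproduce the plan's sample sizes.** One-sample normal formula:

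n = [(1.960·√(p0(1−p0)) + 0.842·√(p1(1−p1))) / (p1−p0)]²

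- 25% vs 5%: [(0.4272 + 0.3644)/0.20]² = 15.67, so 16.
- 10% vs 5%: [(0.4272 + 0.2525)/0.05]² = 184.77, so 185.

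Both figures reproduce with 5% as the null. The sample size is therefore not at fault. It was worked out for a different hypothesis from the one in section 6.3.

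**2. What would count as significant against zero?** Section 10.2 assigns no test, so three readings are taken as assumptions:

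- Literal null of exactly zero: 1 participant with an attempt is enough.
- Uncorrected chi-square against 0/n: 4 are needed (p=0.044 at n=185, 0.0445 at n=220; 3 gives 0.082). Uncorrected McNemar also needs 4.
- Exact McNemar: 6 are needed (2·0.5⁶ = 0.031; 2·0.5⁵ = 0.0625). Fisher against 0/n also needs 6 (p=0.030; 5 gives 0.061).

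**3. Chance of significance against zero when the true rate is only 5%** (binomial upper tail):

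| Participants needed | n=185 | n=220 |
|---|---|---|
| 1 | >99.9% | >99.9% |
| 4 | 98.4% | 99.6% |
| 6 | 90.4% | 96.6% |

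**4. What would count as significant against 5%?** Score test, z = (x/n − 0.05)/√(0.05·0.95/n), two-sided 0.05:

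- n=185: 15 gives z=1.94, 16 gives z=2.28. The bar is 16 (8.6%), upper-tail probability 0.024.
- n=220: 17 gives z=1.86, 18 gives z=2.17. The bar is 18 (8.2%), upper-tail probability 0.029.

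**5. Where the two nulls disagree.** With six needed against zero, counts of 6–15 of 185 (3.2–8.1%) or 6–17 of 220 (2.7–7.7%) are significant against zero but not against 5%. At a true rate of 5% these ranges occur with probability 88% and 94%. An extreme illustration with four needed: 4 of 220 (1.8%) is significantly above zero (p=0.0445) and significantly below the plan's own 5% (z=−2.17, p=0.030).

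**6. At the planning value.** If the true rate is 25%, the chance of missing the bar against 5% is about 3×10⁻⁹ at n=185 and 3×10⁻¹¹ at n=220.

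**7. How firm is 5%?** Simple division gives 65.4/12 = 5.45%. A constant hazard (an assumption) gives 1 − (1−0.654)^(28/365) = 7.8% per 28 days. If the true background is 7.8%, the score test against 5% rejects 37.5% of the time at n=185 and 45.6% at n=220. Against 7.8% the bars become 22 of 185 and 26 of 220, power at 25% is still above 99.9%, and the formula in step 1 gives n=27 instead of 16.

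**The case against.** The strongest reply is that little depends on this. The endpoint is secondary, the sample size and data collection are unaffected, and at 25% both nulls are rejected. The 88–94% figures describe a sensor with no effect, which is not what the sponsor expects. This stands as a limit on weight. It does not remove the problem, because 25% comes from interim pilot results and a pre-specified comparator has to be informative across the results that could occur.

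A second reply is that 5% is itself a weak comparator: step 7 shows that a test against it can reject too often, and in a single-arm study rejecting 5% does not isolate the sensor either. This also stands. It is a reason to justify the 5%, to show the interval against a range, and to word the conclusion as a comparison with a benchmark. It is not a reason to keep zero, which ignores the background altogether.

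Third, sections 7.7 and 8 show that quit attempts are recorded at registration and for the past 12 months, so a background rate could come from the participants themselves. That is a reasonable supplement, but the plan specifies no such comparison for this endpoint.

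Finally, a one-sample chi-square against 5% is the square of the score test, so section 10.2 already covers the type of test. What it mainly lacks is the test value.

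**Conclusion.** The concern holds. Sections 6.3 and 6.6 give different null values for the same endpoint, section 10.2 does not reconcile them, and the value in section 6.3 is one that background attempts alone would reject with probability between 90% and more than 99.9%, depending on the test and the analysed n.

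These probabilities rest on three assumptions: a true rate equal to the plan's 5%, one of the three readings of the comparison with zero, and an analysed n of 185 to 220. The practical effect is confined to observed rates below about 8%. This should be fixed before analysis. It does not threaten the sample size or the primary endpoint.

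**What to change.** **Section 6.3.** Replace the comparison with zero by a comparison with the 5% monthly background rate of section 6.6, using a two-sided one-sample score test at 0.05, reported with the Wilson (score) 95% confidence interval. This interval agrees with the test. An exact interval need not: at 18 of 220 the score test rejects 5%, with Wilson interval 5.2–12.6%, while the exact interval is 4.9–12.6%. If an exact test is preferred, name it together with the exact interval; its bars are 16 of 185 and 19 of 220.

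**Section 10.2.** Name this test and test value for the endpoint. State the analysed n and whether the completer or the carried-forward analysis governs. Say that the no-change comparator does not apply to this endpoint, and that the separate rule for missing data is unaffected.

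**Section 6.6.** State how 65.4% a year becomes 5% a month, and report the confidence interval against the range 5–7.8%.

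**Reporting.** Describe the result as a comparison with an external benchmark, not as proof of a sensor effect. The study has one arm, pays participants (section 6.5), and sets a minimum share who plan to quit within 30 days (quota table in section 6.3).

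**Related clarification, not an error.** Section 6.6 sizes the endpoint of at least 50% CPD reduction "to show a difference from 5" percent. Carry that test value and the same test into sections 6.3 and 10.2. The planning formula gives 80% power at n=185; the binomial power of the score test at 10% vs 5% is 76% at n=185 and 84% at n=220, so the power statement should name the test and the analysed n.

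**Cost.** Wording only, with no added enrolment. The bar for quit attempts rises from 1, 4 or 6 participants, depending on the reading, to 16 of 185 or 18 of 220. Power at 25% stays above 99.9%.

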### 6.2 STUDY DURATION

The study will run for 84 days (+ up to 14 days to obtain completion of the final questionnaire), with questionnaires emailed at baseline, 7, 14, 21, 28, 56 and 84 days.

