### **7.5 DAYS 1 THROUGH 84 – STUDY QUESTIONNAIRES**

Participants will receive periodic electronic questionnaires via email (Survey Monkey) that focus on attitudes towards quitting, smoking behavior, and participant feedback on breath sensor set-up, user experience, impact and commercialization (Section 7.7).

Participants will receive periodic reminders from study staff to complete the questionnaires via email, text or phone, as needed. All participants will receive the 28-day and 84-day questionnaires, regardless of previous completion of questionnaires.

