### **7.6 DAY 84 AND STUDY COMPLETION**

Upon completion of the study, the participant will receive the electronic final questionnaire; the participant will have up to 14 days to complete the final questionnaire once it has been emailed to them. The participant will be asked to send the Pivot Breath Sensor back using a provided pre-paid mailer.

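### The quit-attempt item behind the day 28 secondary endpoint has no end date, so a late answer can count attempts made after day 28

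*Combined protocol and SAP*

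**What the plan says.** Section 6.3 gives the endpoint its time limit and comparator in one line: "quit attempt by day 28; will be compared to zero". It then defines a quit attempt as an answer of one or more to a single item, which opens "Since you began using the Pivot Breath Sensor, how many times have you tried to quit smoking". The item has a start (first use of the sensor) and no end.

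Section 6.2 gives the timing of the surveys: "up to 14 days to obtain completion of the final questionnaire), with questionnaires emailed at baseline, 7, 14, 21, 28, 56 and 84 days". The listed days are mailing days. Section 7.6 repeats the one completion limit: "the participant will have up to 14 days to complete the final questionnaire once it has been emailed to them". No such limit is visible for the day 28 questionnaire.

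Section 7.5 describes follow-up of non-responders: "Participants will receive periodic reminders from study staff to complete the questionnaires via email, text or phone, as needed". It adds that everyone is sent the day 28 questionnaire, including those who missed earlier ones.

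Section 8 lists quit attempts in the past 12 months and during the study, without dates. Section 10.2 asks completers only for a baseline and an outcome response, with no visit window. For missing categorical data at day 28 it carries the last post-baseline response forward, and if there is none it treats the participant as unchanged.

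Section 6.6 plans on 25% of participants making an attempt, set against a general-population figure: "the average monthly quit attempt rate is approximately 5" per cent.

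**The concern.** The label fixes exposure at 28 days, but the item measures exposure up to the moment of answering. Take a participant who first tries to quit on day 40 and returns the day 28 questionnaire on day 45. That person truthfully answers one, and if the response is accepted is scored as having attempted by day 28. Since section 8 lists no attempt dates, the error could not be undone at analysis.

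For any one responder, a longer window can only raise the chance of at least one attempt, so late answers push the completer proportion in one direction. The study has no control arm that would share the shift. A reader who sets the result beside the monthly rate in 6.6 would be comparing different lengths of time.

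**Working it through.** **Inputs.** From 6.6: planned proportion 25%, reference 5%, power 80%, significance level 0.05, enrolment up to 220. Assumed, because the documents do not give them: the delay in answering, the share who answer late, and a constant rate of first attempts. The 5% and 25% are taken as 28-day probabilities.

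**The plan's own figure.** One-sample test of a proportion, two-sided, normal approximation:

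n = [(1.96·√(0.05·0.95) + 0.842·√(0.25·0.75)) / (0.25 − 0.05)]² = [(0.427 + 0.364) / 0.20]² = 15.67, so 16.

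This reproduces n=16. The same formula gives 184.8, so 185, for the 10% versus 5% cigarette-reduction endpoint. The figure stands on its inputs, and the point here does not alter it.

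**One responder.** With a constant rate, the chance of at least one attempt by day t is p(t) = 1 − (1 − p28)^(t/28).

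| Day answered | Delay (days) | True 28-day 5% becomes | True 28-day 25% becomes |
|---|---|---|---|
| 28 | 0 | 5.0% | 25.0% |
| 35 | 7 | 6.2% | 30.2% |
| 42 | 14 | 7.4% | 35.0% |
| 55 | 27 | 9.6% | 43.2% |

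The last row is an outer illustration: it supposes an answer the day before the day 56 mailing.

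**The whole study.** If a share f answers late, the reported proportion is (1 − f)·p28 + f·p(t).

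| Share late | Delay (days) | 5% reads as | 25% reads as |
|---|---|---|---|
| 20% | 14 | 5.5% | 27.0% |
| 25% | 7 | 5.3% | 26.3% |
| 25% | 14 | 5.6% | 27.5% |
| 50% | 14 | 6.2% | 30.0% |

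For example, 0.80·0.25 + 0.20·0.350 = 0.270, and 0.75·0.05 + 0.25·0.074 = 0.056.

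**Effect on a test against 5%, if one were made.** With 220 participants, an exact two-sided test at 0.05 rejects upward at 19 or more attempters. Under a true 28-day rate of 5% the chance of that is 1.5%. It becomes 4.2% if a quarter answer 14 days late, and 9.2% if half do.

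**The opposite pull.** In the schedule (7.7) the quit-attempt survey before day 28 is at day 14. A day 14 answer carried forward covers about 14 days: 1 − 0.95^(14/28) = 2.5% in place of 5%, and 1 − 0.75^(14/28) = 13.4% in place of 25%. At a true 25%, a carried-forward participant contributes 11.6 points too little (25 − 13.4), and a participant 14 days late about 10 points too much (35.0 − 25). Similar numbers of each would nearly cancel.

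**The case against.** The strongest reply is that the item defines what an attempt is, while the words by day 28 separately set the time limit. Read literally, an answer given on day 45 was not reported by day 28 and would go to the missing-data rule. A reader might infer that the plan, followed as written, produces a wrong value. The documents do not support that: no section says a late answer is accepted as the day 28 response, and none says it is refused. The text is silent, and the bias arises only under the first choice. That silence still matters, because staff have to choose.

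A deadline might also sit in material that is not shown, such as the follow-up questionnaires or the consent form that sets out the payment bundles. So the fair statement is that no day 28 limit is visible. The item itself is quoted in full, so its missing end date is not a matter of redaction.

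Third, 6.3 compares the proportion with zero, and the 5% rate appears only in the sample-size reasoning. Against zero, a longer window hardly changes the test. Against 5%, the planned contrast of 25% is wide enough to survive moderate lateness. Both points stand. They limit the matter to the accuracy of the reported proportion and its comparison with a monthly rate. The two comparators are a separate question.

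**Conclusion.** The point holds as an undefined end of exposure. The endpoint promises attempts by day 28, the item does not stop at day 28, and nothing visible in 6.2, 7.5, 7.6, 8 or 10.2 closes the gap. If late answers are accepted, the completer proportion is biased upward.

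The size is probably modest: roughly 1 to 3 points on 25%, and 0.3 to 0.6 points on 5%, when 20 to 25% of participants answer 7 to 14 days late. This rests on a constant rate and on assumed lateness.

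Two stronger readings are tempting and should be resisted. A reader might take 35% or 43% as the likely study result, but those are probabilities for an individual who answers 14 or 27 days late. A reader might also conclude that the bias is upward in every analysis. In the imputed analysis, carried-forward day 14 answers act downward, and the net direction is unknown. Neither the comparison with zero nor n=16 is undermined. This is a cheap improvement to the definition, not a threat to the study's conclusion.

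**What to change.** In 6.3, add one survey line asking for the date of the first quit attempt, or reword the item so that it ends at the participant's own day 28 date. Count only attempts on or before day 28. Either form keeps late responders in the analysis at the right exposure.

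A response window alone is a weaker remedy. A window of day 28 to 35 would still allow 35 days of exposure (30.2% in place of 25% for someone answering on the last day). It would also send later answers to day 14 carry-forward or to unchanged, losing true attempts made between days 15 and 28.

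In 10.2, record and report the completion day of the day 28 questionnaire, and add a sensitivity analysis limited to answers given close to day 28.

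The cost is one survey line, a sentence or two in 6.3 and 10.2, and some recall error in the reported dates. The documents do not say that questionnaire completion dates are kept. An electronic survey would be expected to provide them, but this is an assumption to confirm.
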